### 8.2 Lost to Follow-Up

A participant will be considered lost to follow-up if he or she repeatedly is unable to be contacted by the study site.

Before a participant is deemed lost to follow up, the investigator or designee must make every effort to regain contact with the participant, where possible, with two telephone calls, or a message to the participant's last known mailing address or local equivalent methods. These contact attempts should be documented in the participant's medical record with possible reasons lost to follow-up, if available.

## **9 ADVERSE EVENTS AND DEVICE DEFICIENCIES**

### **9.1 Definitions of Events**

#### **9.1.1 Adverse Events (AEs)**

An adverse event is defined as any untoward medical occurrence, unintended disease or injury, or untoward clinical signs (including abnormal laboratory findings) in participants, users, or other persons, whether or not related to the investigational medical devices or procedure and whether anticipated or unanticipated (ISO 14155:2020).

Pre-existing conditions should be considered as part of the participant's medical history and should not be reported as an AE unless there is a substantial increase in severity or frequency of the condition, which has not been attributed to natural history. Likewise, planned hospital visits and/or hospital stays should not be considered as adverse events. Exacerbation of an existing condition should be reported as an AE if the event meets the protocol definition of an AE.

The clinical course of the event will be followed according to accepted standards of medical practice until the event resolves, stabilizes, or in the opinion of the Investigator, is no longer considered clinically significant. The Investigator must supply the Sponsor with information concerning the follow up and/or resolution of the AE.

#### **9.1.2 Serious Adverse Events (SAEs)**

A serious adverse event is defined by ISO 14155:2020 as an adverse event that led to any of the following:

- a. death;
- b. serious deterioration in health of the participant, users, or other persons as defined by one or more of the following:
  1. a life-threatening illness or injury, or
  2. a permanent impairment of a body structure or a body function including chronic diseases, or
  3. in-patient or prolonged hospitalization, or
  4. medical or surgical intervention to prevent life-threatening illness or injury or permanent impairment to a body structure or a body function,
- c. fetal distress, fetal death, or a congenital abnormality or birth defect including physical or mental impairment.

Planned hospitalization for a pre-existing condition, or a procedure required by the protocol, without serious deterioration in health, is not considered a serious adverse event.

### 9.1.3 Adverse Device Effect (ADE) / Serious Adverse Device Effect (SADE)

An adverse device effect is defined as any adverse event that is considered to be related to the use of an investigational medical device. This definition includes any event resulting from insufficiencies or inadequacies in the instructions for use, deployment, implantation, installation or operation or any malfunction of the investigational device (study device) and includes any event that is a result of a user error or intentional misuse of the investigational medical device.

A serious adverse device effect (SADE) is defined as an ADE that has resulted in any of the consequences characteristic of an SAE.

### 9.1.4 Unanticipated (Serious) Adverse Device Effect (UADE/USADE)

An unanticipated (serious) adverse device effect (UADE/USADE) is any (serious) adverse device effect on health or safety or any life-threatening problem or death caused by, or associated with, a study device, which by its nature, incidence, severity, or outcome has not been identified in the current instructions for use and/or current version of the risk analysis report, or any other unanticipated serious problem associated with a device that relates to the rights, safety or welfare of participants.

UADEs/USADEs will be reported to the appropriate governing body per ISO 14155:2020.

Anticipated serious adverse device effect (ASADE) is an effect which by its nature, incidence, severity or outcome has been identified in the risk assessment.

## 9.2 Severity of Adverse Events

Each AE shall be assessed for its severity, or the intensity of an event, experienced by the participant according to the criteria below.

Severity Rating	Description
Mild	Event, signs, or symptoms that do not interfere with the participant's daily activity, are usually considered self-limiting, can be treated with non-prescription type medications, and do not require medical intervention
Moderate	Event may interfere or cause low level inconvenience with the participant's daily activity. Requires medical intervention and/or treatment; however, unlikely to require hospitalization or be considered potentially life-threatening in nature
Severe	Event may cause significant discomfort to the participant and/or interferes with the participant's daily activity. Requires medical intervention and/or treatment to preclude a permanent impairment; may be life threatening and/or require hospitalization

## 9.3 Relationship of Adverse Event to Device(s)/Procedure

Each AE will be assessed for its relationship to the study device or procedure according to the following guidelines.

A. Assess each AE for its relationship to the device or procedure.

- Device Related: This category should be restricted to AEs directly attributable to the study devices used.
- Procedure: A procedure includes any study-related activity performed during the neuraxial procedure.

B. The following categories shall be used for assigning the certainty of the relatedness.

Relatedness	Description according to MDCG 2020-10/1
Not Related	
Relationship to the device, comparator or procedures can be excluded when:
 
 
• The event has no temporal relationship with the use of the investigational device, or the procedures related to application of the investigational device;
 
• The AE/SAE does not follow a known response pattern to the medical device (if the response pattern is previously known) and is biologically implausible;
 
• The discontinuation of medical device application or the reduction of the level of activation/exposure - when clinically feasible - and reintroduction of its use (or increase of the level of activation/exposure), do not impact on the AE/SAE;
 
• The event involves a body-site or an organ that cannot be affected by the device or procedure;
 
• The AE/SAE can be attributed to another cause (e.g. an underlying or concurrent illness/ clinical condition, an effect of another device, drug, treatment or other risk factors);
 
• The event does not depend on a false result given by the investigational device used for diagnosis^, when applicable;
 
 
In order to establish the non-relatedness, not all the criteria listed above might be met at the same time, depending on the type of device/procedures and the serious adverse event.
 
^If an investigational device gives an incorrect diagnosis, the patient might, for example, receive an unnecessary treatment and incur all the risks that accompany that treatment, or might be incorrectly diagnosed with a serious disease. In other cases, the patient might not receive an effective treatment (thereby missing out on the benefits that treatment would confer) or might not be diagnosed with the correct disease or condition.

Possible	
The relationship with the use of the investigational device or comparator, or the relationship with procedures, is weak but cannot be ruled out completely. Alternative causes are also possible (e.g., an underlying or concurrent illness/ clinical condition or/and an effect of another device, drug, or treatment). Cases where relatedness cannot be assessed, or no information has been obtained should also be classified as possible.

Relatedness	Description according to MDCG 2020-10/1
Probable	
The relationship with the use of the investigational device or comparator, or the relationship with procedures, seems relevant and/or the event cannot be reasonably explained by another cause.

Causal relationship	
The AE/SAE is associated with the investigational device, comparator or with procedures beyond reasonable doubt when:
 
 
• The event is a known side effect of the product category the device belongs to or of similar devices and procedures;
 
• The event has a temporal relationship with investigational device use/application or procedures;
 
• The event involves a body-site or organ that 
 
◦ the investigational device or procedures are applied to;
 
◦ the investigational device or procedures have an effect on;
 
 
 
• The AE/SAE follows a known response pattern to the medical device (if the response pattern is previously known);
 
• The discontinuation of medical device application (or reduction of the level of activation/exposure) and reintroduction of its use (or increase of the level of activation/exposure), impact on the AE/SAE (when clinically feasible);
 
• Other possible causes (e.g. an underlying or concurrent illness/clinical condition or/and an effect of another device, drug or treatment) have been adequately ruled out;
 
• Harm to the subject is due to error in use;
 
• The event depends on a false result given by the investigational device used for diagnosis^^, when applicable;
 
 
In order to establish the relatedness, not all the criteria listed above might be met at the same time, depending on the type of device/procedures and the serious adverse event.
 
^^If an investigational device gives an incorrect diagnosis, the patient might, for example, receive an unnecessary treatment and incur all the risks that accompany that treatment, or might be incorrectly diagnosed with a serious disease. In other cases, the patient might not receive an effective treatment (thereby missing out on the benefits that treatment would confer), or might not be diagnosed with the correct disease or condition.

## 9.4 Reporting of Events

For all adverse events, all sections of the appropriate Case Report Form (CRF) must be completed, reporting the date of the adverse event, resolution, action taken, assessment of both the seriousness and the relationship to the study devices and the related procedure. Additional information may also be collected if appropriate.

- All SAEs, SADEs, and/or UADEs/USADEs must be reported to the Sponsor via electronic CRF without unjustified delay and within three (3) calendar days of the site/investigator becoming aware of the event.

- De-identified copies of all requested relevant documentation should be submitted to the Sponsor within 72 hours of knowledge, as appropriate.
- Only in case the eCRF system is not operational, the SAEs and (U)SADEs can be sent to the Sponsor per e-mail to the e-mail address [[contact]](mailto:[contact])
- Safety related correspondence or questions can be addressed to following contact. BD Trial Safety Team, email: [[contact]](mailto:[contact])

It is the responsibility of the Investigator to report adverse events to individual Institutional Review Boards (IRBs)/Ethics Committees (ECs) and/or regulatory authorities according to the local regulations in each participating country. The Sponsor or their designee is responsible for reporting AEs to regulatory authorities according to the local regulations in each participating country.

## **9.5 Safety Committees**

A safety committee will not be used for this study.

## **9.6 Device Deficiencies**

The Investigator will record a device deficiency if a device used in the study, which appeared to be inadequate with respect to its identity, quality, durability, reliability, usability, safety or performance whether due to mechanical failure, malfunction, or defect. Device deficiencies also include use errors and inadequate labeling. This applies to: devices used to treat the participant, or devices in which the package was opened, but the device was not used for treatment, or devices with which treatment was attempted, but the device did not remain through the entire study procedure/period.

All device deficiencies will be recorded on the appropriate Case Report Form and will be promptly reported to the Sponsor. The device(s) should be returned to the Sponsor if requested.

If the device deficiency was associated with an AE, the reporting provisions for AEs, ADEs, SAEs, SADEs and UADEs/USADEs apply.

Reported deficiencies will be investigated and reported under 21 CFR part 803 Medical Device Reporting by the Sponsor if necessary, or as required by appropriate national laws and regulations. The site may be contacted to provide additional information to allow the Sponsor to conduct a thorough investigation.

It is the responsibility of the Investigator to notify the IRB/EC of such device deficiencies in accordance with the IRB/EC and/or the Competent Authority's local regulations.

## **9.7 Serious Health Threat**

During the course of the study, device deficiencies or adverse events will be assessed if they constitute a serious health threat. The serious health threat is a signal from any adverse event or device deficiency that indicates an imminent risk of death or a

serious deterioration in the health in subjects, users or other persons, and that requires prompt remedial action for other subjects, users or other persons. Serious health threat includes the

possibility of multiple deaths occurring at short intervals, or other significant and unexpected serious adverse events that can be regarded as a potential serious health hazard in subjects, users or other persons and which are possibly related to the investigation device use.

## 10 STATISTICAL METHODS

The statistical analysis plan will be finalized prior to database lock and will include a more technical and detailed description of the statistical analyses described in the following sections. This section includes a summary of the planned statistical analyses of the most important endpoints including primary endpoints.

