Investigational Sites	Up to 10 sites within Europe will participate in this study. No more than 25% of participants may be enrolled at any one site.

Data Monitoring Committee	A Data Monitoring Committee will not be used in this study.
Regulatory Status	The BD Spinal NRFit™ Needles, BD Spinal Introducer NRFit™ Needle, BD Spinal NRFit™ Needle Sets, BD Syringes NRFit™, BD Blunt Fill NRFit™ needle and BD Blunt Filter NRFit™ needle are currently CE marked and marketed in the EU.

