## 4 STUDY DESIGN

### 4.1 Overall Design

This is a multi-center, prospective, open label, single arm post-market study that will enroll approximately 180 participants in order to have a minimum of 150 treated participants who will receive a spinal anesthesia procedure as part of their routine medical care. A minimum of 50 participants for each of the two needle tip types (Quincke and Whitacre tip) will be enrolled in the study. Data related to the safety and performance of the BD Spinal NRFit™ Needles, the BD Spinal Introducer NRFit™ Needles, the BD Spinal NRFit™ Needle Sets, the BD Syringes NRFit™ and ancillary devices will be captured when used as intended.

Participants will be screened against eligibility criteria and will be considered enrolled once the informed consent document is signed. The procedure(s) performed, and device(s) used, will be left to the discretion of the participant's physician investigator.

Participants will be followed from the time of spinal procedure for up to 10 days ( $\pm$  3 days) post spinal procedure to assess for any adverse events/complications. If the participant has been discharged from the hospital prior to day-10 ( $\pm$  3 days) post procedure, follow-up may be performed in a variety of ways including by telephone. The site staff must take advantage of the time window of  $\pm$  3 days only when the 10-day post-procedure occurs during the weekends or holidays. However, any adverse event or complication must be diagnosed and confirmed by a study physician.

Additionally, to assess overall ease of spinal procedure, the clinician performing the procedure will complete a brief survey describing their experience with the procedure.

The total duration of the study is expected to be approximately 49-51 weeks from first participant enrolled up to last participant having last visit.

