#### 10.5.1.2 Performance of the BD NRFit™ Syringes

- Rate of successful aspiration and injection of anesthetic through BD NRFit™ Syringes
- Rate of BD NRFit™ Syringes that do not leak at the connection point during medication administration

The incidence rate for the primary performance endpoints will be calculated as the number of participants experiencing the event divided by the total number of treated participants; 95% confidence interval (exact method) will be calculated.

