# 11 DATA COLLECTION AND RECORD MAINTENANCE

## 11.1 Case Report Forms

The Investigator is responsible for ensuring the completeness and accuracy of all study documentation.

All required clinical data will be collected/document in sponsor-provided electronic Case Report Forms (CRFs). Applicable national and local regulations are followed on the handling of electronic data. Modification of the CRFs will only be made if deemed necessary by the Sponsor and/or the appropriate regulatory body. The site must complete the eCRFs according to the participant's visit on an ongoing basis to allow regular review by the Sponsor or their designee, within approximately three (3) days of the site/investigator is aware of the data.

Site numbers and participant numbers will be used to track participant information throughout the study. Participant personal information will be pseudonymized/de-identified.

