2.3 Randomization and Blinding

This is a single-arm and open label study, randomization and blinding are not applicable.

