2.5 Interim Analysis

No interim analysis is planned for the study.

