5.2.1.2 Performance of the BD NRFit™ Syringes

- Rate of successful aspiration of anesthetic through BD NRFit™ Syringes

A subject will be included in the analysis population if the following condition is met:

- Spinal Procedure Details – Syringe CRF page: 'Was a BD syringe NRFit used?' Equals 'Yes'

A successful aspiration of anesthetic through BD NRFit™ Syringe is defined as follows:

- 'Was anesthetic medication successfully aspirated through the BD NRFit syringe?' Equals 'Yes'

The incidence rate for this endpoint will be calculated as the number of participants experiencing the event divided by the total number of treated participants using the BD NRFit™ Syringes; 95% confidence interval (exact method) will be calculated.

- Rate of successful injection of anesthetic through BD NRFit™ Syringes

A subject will be included in the analysis population if the following condition is met:

- Spinal Procedure Details – Syringe CRF page: 'Was a BD syringe NRFit used?' Equals 'Yes'

A successful injection of anesthetic through BD NRFit™ Syringe is defined as follows:

- 'Was anesthetic medication successfully injected through the BD Syringe NRFit?' Equals 'Yes'

The incidence rate for this endpoint will be calculated as the number of participants experiencing the event divided by the total number of safety population using the BD NRFit™ Syringes; 95% confidence interval (exact method) will be calculated.

 BD	Statistical Analysis Plan	Page No.
	Study ID: MDS-21NRFit001	9 of 13

GFM-10082C

- Rate of BD NRFit™ Syringes that do not leak at the connection point during medication administration
A subject will be included in the analysis population if the following condition is met:
 - Spinal Procedure Details – Syringe CRF page: 'Was a BD syringe NRFit used?' Equals 'Yes'
A success of the endpoint for the BD NRFit™ Syringe is defined as follows:
 - 'Did the BD Syringe NRFit leak at the connection point during medication administration?' Equals 'No'

The incidence rate for this endpoint will be calculated as the number of participants experiencing the event divided by the total number of safety population using the BD NRFit™ Syringes; 95% confidence interval (exact method) will be calculated.

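### The SAP need only be final by database lock in an unmasked study, and its syringe section replaces the protocol's joint endpoint and two denominators without recording the change

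*Protocol*

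**What the plan says.** Protocol Section 10 sets one limit on timing: "The statistical analysis plan will be finalized prior to database lock". It presents the SAP as a fuller technical account of analyses that the protocol already outlines.

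On masking, SAP 2.3 states: "This is a single-arm and open label study, randomization and blinding are not applicable". Protocol 11.1 has sites complete eCRFs "on an ongoing basis to allow regular review by the Sponsor or their designee", within about three days of knowing the data. The Protocol synopsis adds "A Data Monitoring Committee will not be used in this study", and SAP 2.5 says "No interim analysis is planned for the study". Neither document restricts the SAP authors' access to outcome data.

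Protocol 10.5.1.2 has two syringe endpoints. The first is joint: "Rate of successful aspiration and injection of anesthetic through BD NRFit™ Syringes". The second is absence of a leak at the connection point. Both are divided by all treated participants.

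SAP 5.2.1.2 has three syringe rates. Aspiration is taken over treated syringe users. Injection and no-leak are each "divided by the total number of safety population using the BD NRFit™ Syringes". SAP 4.1 defines the safety population by spontaneous CSF at the hub, yet assigns the primary performance endpoints to the treated population. SAP Table 1 keeps the joint endpoint. SAP 1.3 keeps one limit for aspiration/injection, more than 80%, and a leak limit of less than 2%.

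**The concern.** Finalising a SAP before lock guards against data-driven choices when outcomes are masked until lock. In a one-arm, unmasked study each eCRF entry on CSF, injection or leak is itself an endpoint result, so lock hides nothing from anyone who can read the eCRFs. The absence of an interim analysis limits formal looks, not access.

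That would matter little if the SAP kept the protocol's definitions. For the syringes it does not, and it has no section that records departures from the protocol. Success is judged by setting observed rates against fixed limits (SAP 1.3). Such a comparison is pre-specified only if the numerator and denominator were fixed before the outcomes could be seen. As written, the protocol's joint syringe rate on treated participants is never computed, and the reader is not told that it was replaced.

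**Working it through.** The plan gives no figure of its own on this point, so the definitions come first and then an illustration.

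| Item | Protocol 10.5.1.2 | SAP 5.2.1.2 | Elsewhere in the SAP |
|---|---|---|---|
| Aspiration and injection | one joint rate | two separate rates | Table 1: joint |
| Denominator, aspiration | treated | treated syringe users | 4.1: treated |
| Denominator, injection | treated | safety-population syringe users | 4.1: treated |
| Denominator, no-leak | treated | safety-population syringe users | 4.1: treated |
| Limit for aspiration/injection | more than 80% (Protocol 3.1) | none stated | 1.3: more than 80%, one limit |

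**Inputs.** 150 treated is the planned minimum. 135 with CSF is 0.90 × 150, using the placement rate in the plan's precision table. The remaining counts are assumptions: all 150 use the syringe, 133 of the 135 are injected successfully, those 133 were also aspirated successfully, and the 15 without CSF count as not injected.

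**Injection**
- Protocol denominator: 133/150 = 88.7%. Under these assumptions this is also the joint rate.
- SAP denominator: 133/135 = 98.5%.
- Difference: 98.52 − 88.67 = 9.85, or 9.9 points. Both exceed 80%.

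**When the denominator alone would cross 80%**
- If everyone with CSF is injected successfully, 120 with CSF gives 120/150 = 80.0% (exact 95% CI 72.7 to 86.1), which does not exceed 80%. The SAP gives 120/120 = 100% (97.0 to 100). Placement would then be 80% and would already miss its own limit of at least 90%.
- With 135 with CSF, the SAP rate passes from 109 successes (109/135 = 80.7%) and the protocol rate fails up to 120 (120/150 = 80.0%). The two disagree for 109 to 120 successes, that is, 15 to 26 failed injections among the 135.

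**Splitting the joint endpoint.** Suppose all 150 have CSF, so every denominator is 150, and aspiration and injection each succeed in 130 (86.7%). The joint count lies between 130 + 130 − 150 = 110 and 130, so the joint rate lies between 73.3% and 86.7%. Both parts can pass while the joint endpoint fails. The lower end is a mathematical bound. If injection can succeed only after successful aspiration, the joint rate equals the injection rate.

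**Leak.** With 2 leaks, both among those with CSF, incidence is 2/150 = 1.3% or 2/135 = 1.5%. Both are under 2%, and the SAP denominator is slightly stricter. With 3 leaks the figures are 2.0% and 2.2%, and neither is under 2%.

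**The case against.** The strongest reply is that the protocol already fixed the endpoints, populations, exact intervals, last-attempt rule and limits, and that the SAP leaves the limits discussed here unchanged. Finalising before lock breaches nothing. Protocol 11.1 describes review of eCRF data, not tabulation of rates. Protocol 10.4 restricts analyses to evaluable data and names procedures not performed as a source of missing endpoints, so a participant who received no injection may not belong in the denominator. On that reading 133/150 is not clearly the protocol's result. What remains would be an inconsistency of text, to be reconciled whatever the SAP's date.

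Much of this stands. The 9.9 points depend on how evaluable is read, and no acceptance decision changes in the main illustration. It does not answer the split of the joint endpoint, the SAP's conflict with its own Table 1 and Section 4.1, or the lack of a rule for the 80% limit.

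Four stronger readings are tempting, and the documents do not support them.
- *Definitions were chosen after seeing data.* Nothing shows this. The available SAP text carries version 1.0 and no date, but a page bearing the date may simply not be public.
- *Every change favours the device.* If the 15 participants without CSF are recorded as having no leak, no-leak is 148/150 = 98.7% on the protocol denominator and 133/135 = 98.5% on the SAP's.
- *Leak incidence falls from 11.3% to 1.5%.* The 11.3% is the complement of 133/150 and counts 15 participants without CSF as leaks.
- *The introducer rate was redefined too.* Protocol 10.5.1.1 already names an introducer population and Protocol 10.2 plans about 100 such participants. The SAP denominator is a clarification.

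**Conclusion.** The point holds in a limited form. The timing rule permits definitions to be settled with outcomes in view, although nothing shows that this happened. SAP 5.2.1.2 changes the joint syringe endpoint and the denominators for injection and no-leak. It conflicts there with Protocol 10.5.1.2, SAP Table 1 and SAP 4.1, and leaves the single 80% limit without a stated rate.

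On the assumed counts the injection rate moves by 9.9 points, from 88.7% to 98.5%, with both above the limit. This rests on participants without CSF being counted as not injected. Leak incidence changes by about 0.1 to 0.2 points. There is no hypothesis test, and the exact intervals remain valid for whatever rate is computed. What is lost is the assurance that the rate was fixed in advance.

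**What to change.** 1. In Protocol Section 10, require the SAP to be final before outcome data are reviewed, preferably before the first participant is treated. Any later change should be a dated SAP amendment with its reason. If treatment has begun, state in the SAP when version 1.0 was approved relative to the first treated participant.
2. Add an SAP section that lists and justifies each departure from Protocol 10.3 to 10.5. Reconcile SAP 5.2.1.2 with SAP 4.1, SAP Table 1 and Protocol 10.5.1.2.
3. Report the joint aspiration-and-injection rate and the no-leak rate on treated participants beside the SAP-defined rates. State how participants without CSF are counted, and which rate is judged against the 80% limit.

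The cost is earlier completion of the SAP, some wording in both documents and a few table rows. No new data are needed for the joint rate, because the eCRF asks about aspiration and injection separately.
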